8.2.2. Analyses of Other Safety Endpoints

The analyses will be based on the Safety Analysis Set. The 28-Day On-Treatment Time will be applied to all the events of interest, see [Section 7.1.1](#).

The times to the secondary endpoints of opportunistic infection events excluding tuberculosis, tuberculosis, hepatic events, cardiovascular events (MACE and others), serious infections, GI perforations, non-melanoma skin cancers, interstitial lung disease, DVT, PE, ATE, DVT or PE, thromboembolic events (TE) and all-cause mortality will be analyzed by Cox models via univariate model analysis. See [Section 8.1.1](#). The 28-Day On-Treatment Time analysis will be conducted.

The times to herpes zoster events will be analyzed by a multivariate Cox model with region, baseline corticosteroid use, age group, smoking status, treatment as predictors. The 28-Day On-Treatment Time analysis will be conducted.

Unadjusted, or “crude” incidence rates will be calculated as well. Note that the ratios of these rates approximate, but are not exactly equal to, the hazard ratios.

A Surveillance, Epidemiology, and End Results (SEER) analysis of the malignancy endpoint will be conducted. In this analysis, standardized incidence ratio (SIR) for malignancies represents the ratio of the incident number of cases of cancer in the tofacitinib population to the incident number that would be expected if the study population had the same incidence rate as the US population. By way of interpretation, a SIR of more than 1.0 indicates that proportionally more cases of cancer have occurred in the tofacitinib population than the comparator, whereas a SIR of less than 1.0 indicates that proportionally fewer cancer cases have occurred.

The Sponsor has standard (ie, used for all its clinical trials) summary displays and listings for MedDRA-coded adverse events, demography, medical history, length of time in study and discontinuation, concomitant and concurrent medications, physical examination, ECG, laboratory tests, weight, pulse rate, and blood pressure. These standards, called *CaPS (CDISC and Pfizer Standards)*, will be utilized in the reporting of these routine safety variables. For laboratory tests total cholesterol, LDL-c, HDL-c, total cholesterol/HDL-c ratio, LDL-c/HDL-c ratio, Triglyceride, the summary will be produced by subjects on statins, subjects not on statins and subjects on any lower lipid agents including statins.

Only treatment emergent adverse events (TEAE) will be summarized. An event is considered TEAE if the event occurs for the first time during the effective duration of treatment and is not seen prior to the start of treatment or the event is seen prior to the start of treatment but increase in severity during treatment.

No inferential analysis is pre-planned for this set of variables.

These standard summaries of routine safety and subject characteristic data will be organized according to initially randomized group, ie, tofacitinib 5 mg BID, tofacitinib 10 mg BID, tofacitinib combined, and TNFi combined.

For the summaries of TEAE, the treatment emergence for the standard of care will be derived comparing events that happen after switching to the standard of care with events that happen before switching including those after the first dose of randomized treatment.

For subjects who switch from the randomized treatment to standard of care, a separate TEAE table will be presented for these subjects according to their initially randomized group.

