Both total time (ITT) and on treatment analyses of the main safety endpoints will be conducted. The on treatment analysis for MACE will censor subjects who cross over from tofacitinib or adalimumab to standard of care at 60 days after standard of care is initiated. The principal analysis for malignancies will not censor for subjects crossing to standard of care (ie, will be the total time analysis).

Secondary safety endpoints will be summarized according to treatment received at the time of the event.

For the purposes of statistical analyses, subjects who were randomized to tofacitinib 10 mg BID will be maintained in the tofacitinib 10 mg BID treatment arm after reducing the dose of tofacitinib to 5 mg BID.

SCHEDULE OF ACTIVITIES BY VISIT (SCREENING – MONTH 6)

The Schedule of Activities table provides an overview of the protocol visits and procedures. Refer to [Study Procedures](#) and [Assessments](#) sections of the protocol for detailed information on each procedure and assessment required for compliance with the protocol.

The investigator may schedule unplanned visits in addition to those listed on the schedule of activities, in order to conduct assessments required to protect the well-being of the subject.

Protocol Activities – Screening to Month 6	Screen	Visit 1 Day 1	Visit 2 Month ^f 2	Visit 3 Month ^f 3	Visit 4 Month ^f 6
Visit Windows (see Section 6.2.1 for further detail)	NA	See 6.2.1	±2 weeks	±1.5 months	±1.5 months
Informed Consent	X				
Medical History and Confirm Diagnosis	X				
Physical Examination, including height	X				
Assessment of New Physical Findings		X	X	X	X
Weight, Vital Signs	X	X	X	X	X
Inclusion/Exclusion criteria	X	X			
Blood Chemistry ^a , Hematology ^a	X	X	X	X	X
C-reactive Protein (CRP)	X	X	X	X	X
Banked Biospecimens		X			
HIV Serology, HBsAg, HBcAb, HBsAb ^b	X				
HCV Ab, HCV RNA ^c	X				
Lipid Profile (fasting)	X	X	X		
Pregnancy test ^d	X	X	X	X	X
QuantiFERON Gold®™ In-Tube Test	X				
Rheumatoid Factor	X				
Anti-cyclic citrullinated peptide (anti-CCP)	X				
Urinalysis	X				
Chest X-ray	X				
ECG	X				
Randomization		X			
Study Medication Dispensing		X		X	X
Contraceptive Use Documentation	X	X	X	X	X
Joint Count (28)	X	X	X	X	X
Patient Assessment of Arthritis Pain		X	X	X	X
Patient Global Assessment of Arthritis		X	X	X	X
Physician Global Assessment of Arthritis		X	X	X	X
HAQ-DI		X	X	X	X
SF-36 (Version 2, Acute)		X		X	X
EuroQol EQ-5D		X		X	X
Work Productivity and Activity Impairment (WPAI)		X		X	X

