9. DATA ANALYSIS/STATISTICAL METHODS

Detailed methodology for summary and statistical analyses of the data collected in this study will be documented in a Statistical Analysis Plan, which will be maintained by the Sponsor. This document may modify the plans outlined in the protocol; however, any major modifications of the primary endpoint definition and/or its analysis will also be reflected in a protocol amendment.

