9.2. Safety Analysis

9.2.1. Analysis of Primary Safety Endpoint

The co-primary safety endpoints of malignancies and MACE will be analyzed to provide comparative rates for tofacitinib vs. the combined TNFi.

The primary statistical safety objective is the estimation of the hazard ratios relative to the TNFi control for the two tofacitinib doses combined and for each dose of tofacitinib separately for the adjudicated events of MACE and malignancy excluding non-melanoma skin cancer. Analysis of the primary safety endpoints will be based upon adjudicated events.

Hazard ratios for the safety events of main interest will be calculated separately for each primary endpoint. The ratios for both tofacitinib doses combined versus the control, for each tofacitinib dose versus the control, and for the two tofacitinib doses versus each other will be reported along with their 95% confidence intervals. Adjustments for multiplicity will not be applied.

The primary statistical method for deriving estimators for hazard ratios will be the fitting of proportional hazards (Cox) regression models. A model containing only the single independent variable for treatment group will be calculated and reported. The effects of adding other predictors to the model, such as geographic region, age, gender, and so forth will be fully explored and reported. An analysis by TNFi subset strata (ie, the sites/regions where either adalimumab or etanercept was used) will be conducted to assure consistency of results.

A Surveillance, Epidemiology, and End Results (SEER) analysis of the malignancy endpoint will be conducted.

Both total time (or ITT) and on treatment analyses of the main safety endpoints will be conducted. The total time analysis will not censor times to event and will ascribe events to randomized treatment.

The on-treatment analysis for MACE will censor subjects who crossover from tofacitinib, adalimumab or etanercept to standard of care at 60 days after standard of care is initiated. The principal analysis for malignancies will not censor for subjects crossing to standard of care (ie, will be the total time analysis).

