9.2.2. Analysis of Secondary Safety Endpoints

The secondary safety endpoints will include an evaluation of the following events:

- Opportunistic infection events including tuberculosis (adjudicated).
- Hepatic events (adjudicated).
- Cardiovascular events other than MACE (adjudicated).
- All AEs, including SAEs.
- Clinically significant abnormal laboratory parameters.
- All cause mortality (adjudicated).
- Reasons for permanent or temporary discontinuation of study medication.

Adverse events and clinical laboratory abnormalities ([Section 2.2.1.2](#)) will be summarized according to treatment received at the time of the event. Both ITT and on treatment analyses will be conducted for the other secondary endpoints listed in [Section 2.2.1.2](#).

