For the **60-Day On-Treatment Time Analyses** of time-to-event, in addition to the foregoing, when a subject changes from the randomized study treatment to standard of care, the subject’s time to event will be considered censored (censoring time = last dose day of randomized study regimen + the attribution window, or the study day of last on-study contact, whichever is earlier). It will be used for the primary safety endpoint MACE but excluding malignancy (excluding Non-melanoma Skin Cancer (NMSC)), and the attribution window will be 60 days. In other words, the censoring time will be the earliest of study day of last on-study contact, study day of death, and last dose day of randomized study regimen plus 60 days.

For the **Total Time Analyses** of time-to-event, the censoring time will follow the four foregoing listed cases, ie, the censoring time will not change when a subject changes from the randomized study treatment to standard of care. In other words, the censoring time will be the earlier of study day of last on-study contact and study day of death.

For the **28-Day On-Treatment Time Analyses** of time-to-event, in addition to the foregoing, when a subject changes from the randomized study treatment to standard of care, the subject's time to event will be considered censored (censoring time = last dose day of randomized study regimen + the attribution window, or the study day of last on-study contact, whichever is earlier). It will be used for all the secondary safety endpoints, and the attribution window will be 28 days. In other words, the censoring time will be the earliest of study day of last on-study contact, study day of death, and last dose day of randomized study regimen plus 28 days.

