8.2.1. Primary Analysis

Safety endpoint analyses will be carried out using the data collected on the Safety Analysis Set.

Two methods in defining time to an event will be used for the co-primary time-to-event safety endpoints: 60-Day On-Treatment Time and Total Time (see [Section 7.1.1](#) for definitions). The 60-Day On-Treatment Time definition will be used for primary MACE analysis. The Total Time definition will be used for primary malignancies (excluding NMSC).

This primary objective will be addressed via the analysis of the times to these events by proportional hazard (Cox) models via univariate model analysis. See details in [Section 8.1.1](#).

In the time-to-event analyses using a Cox model, the treatment groups will be tofacitinib 5 mg BID, tofacitinib 10 mg BID, and TNFi regimen (adalimumab 40 mg QOW SC and etanercept 50 mg QW SC combined).

Ninety-five percent CIs for the hazard ratios for the combined tofacitinib regimens compared to the TNFi regimen as well as for the 3 pair-wise treatment comparisons, tofacitinib 10 mg BID vs. tofacitinib 5 mg BID, tofacitinib 5 mg BID vs. TNFi, tofacitinib 10 mg BID vs. TNFi, will be presented. For this analysis, only treatment group will be used as an independent variable in the model. For the Total Time analyses changes from original randomized treatment will be ignored. For the 60-Day On-Treatment Time analyses, rules for censoring times to event due to switching from randomized treatment to standard of care are given in [Section 7](#).

Further, multivariate analysis and analysis by TNFi subset strata (ie, the sites/regions where either adalimumab or etanercept was used, in other words, USA/Puerto Rico/Canada as one stratum, the rest as the other stratum) will be conducted to assure consistency of results. No additional analyses comparing adalimumab vs. etanercept will be conducted for the purpose of reporting the primary endpoints of the study; when reporting the primary endpoint analyses, any difference in hazard ratio between the two TNFi controls will be attributed to geographic difference.

These analyses will be used to check the robustness and to assure consistency of the results for primary safety endpoints:

- Models containing independent variable of treatment group adjusted with geographic region, age group, gender, and smoking status (see covariates in [Section 6.4](#)) will be fitted using Safety Analysis Set.

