- *An analysis by TNFi subset strata (ie, the sites/regions where either adalimumab or etanercept was used)* will be performed using Safety Analysis Set.
- The same analyses conducted based on Safety Analysis Set will be conducted using Per Protocol Analysis Set.

Unadjusted, or “crude” incidence rates by Total Time, 60-Day On-Treatment Time and 28-Day On-Treatment Time analysis will be calculated as well.

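### The protocol promises both ITT and on-treatment analyses of all-cause mortality and three other adjudicated secondary endpoints; the SAP plans only 28-day on-treatment Cox models and does not declare the change

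*SAP*

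**What the plan says.** Protocol 9.2.2 divides the secondary safety endpoints into two groups. Adverse events and laboratory abnormalities are summarised by treatment received when the event occurred. For the rest, "Both ITT and on treatment analyses will be conducted for the other secondary endpoints listed in" Protocol 2.2.1.2. That list contains four adjudicated event endpoints: opportunistic infections including tuberculosis, hepatic events, cardiovascular events other than MACE, and all-cause mortality. It also contains reasons for discontinuing study medication.

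Protocol 9.2.1 treats ITT and total time as the same analysis: "The total time analysis will not censor times to event and will ascribe events to randomized treatment".

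SAP 7.1.1 defines Total Time in matching terms, with no censoring at a switch to standard of care and events ascribed to the randomised arm. For the 28-Day On-Treatment definition it then states: "It will be used for all the secondary safety endpoints, and the attribution window will be 28 days". SAP 8.2.2 repeats the assignment ("The 28-Day On-Treatment Time will be applied to all the events of interest") and lists all-cause mortality among the Cox models to be run that way. Total Time Cox models appear only in SAP 8.2.1: "Two methods in defining time to an event will be used for the co-primary time-to-event safety endpoints", these being 60-Day On-Treatment Time and Total Time.

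The Protocol Summary (Safety Analysis) says something different again: "Secondary safety endpoints will be summarized according to treatment received at the time of the event".

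**The concern.** A reader of Protocol 9.2.2 expects a comparison of deaths by randomised arm over all follow-up. The SAP removes it without saying so. Mortality is where this matters most. Protocol 1.2 reports that the communication leading to Amendment 8 included higher all-cause mortality in the 10 mg BID arm than in the other two arms. Protocol 6.2 and 6.7 keep subjects in follow-up after they stop assigned drug, so later deaths are collected. Under SAP 7.1.1 the censoring time is the earliest of last contact, death, and last dose plus 28 days, so a death on day 29 or later after the last dose is not an event in the only planned mortality Cox model.

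Stopping drug is also not random. Protocol 7.15 ties it to laboratory and clinical triggers, and Protocol 13.7 lists adverse events and insufficient response among the reasons. Censoring at that point may therefore be informative. The documents do not show the direction or size of any bias, and none is claimed here. The total-time comparison is the check that would reveal whether the window matters.

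**Working it through.** **1. Passages side by side**

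| Endpoint (Protocol 2.2.1.2) | Promised in Protocol 9.2.2 | Cox model in SAP 7.1.1 and 8.2.2 |
|---|---|---|
| All-cause mortality | ITT and on-treatment | 28-Day On-Treatment only |
| Opportunistic infections, including tuberculosis | ITT and on-treatment | 28-Day On-Treatment only |
| Hepatic events | ITT and on-treatment | 28-Day On-Treatment only |
| Cardiovascular events other than MACE | ITT and on-treatment | 28-Day On-Treatment only |
| Adverse events, laboratory abnormalities | By treatment received | Not at issue |

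The SAP amendment table (SAP section 1) has no entry dropping ITT for secondary endpoints. The nearest entries say that rules for counting time to event were added or moved (version 3) and that the 28-day rule was renamed (version 4).

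**2. Illustration of how much follow-up the 28-day rule leaves out**

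The plan states no figure for this, so there is nothing to reproduce.

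Inputs from the documents:
- Enrolment of 1000, 1500 and 1500 in years 1 to 3, and a study length of about 5 years (Protocol 9.1).
- Annual loss to follow-up of 5%, 3.5%, then 2.5%, stated for malignancies because they are followed after discontinuation; 10%, 7%, then 5% for MACE (Protocol 9.1).
- Discontinuation of assigned treatment of about 15% a year, higher in year 1 (Protocol 13.7).

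Assumptions: uniform entry within each year; constant hazards within each year of follow-up, λ = −ln(1 − p); 20% where year 1 is taken as higher, since the protocol gives no number; and either 15% already includes loss to follow-up or loss comes on top.

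Formulas, averaged over entry time e and summed over the enrolment cohorts:
- Total Time patient-years = Σ n × mean of ∫₀^(5−e) S(t) dt, where S(t) is retention in the study.
- On-treatment patient-years = the same with S(t) × G(t), where G(t) = 1 for the first 28 days and exp[−H(t − 28 days)] after that. H is the cumulative hazard of stopping drug while still followed.
- Share left out = 1 − on-treatment / Total Time.

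For example, −ln(0.85) = 0.1625 a year for stopping and −ln(0.95) = 0.0513 for first-year loss. If the 15% includes loss, the first-year hazard of stopping while still followed is 0.1625 − 0.0513 = 0.1112.

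| Loss to follow-up | Leaving assigned drug | Total Time PY | On-treatment PY | Left out |
|---|---|---|---|---|
| 5/3.5/2.5% | 15%, including loss | 12,557 | 10,359 | 2,198 (17.5%) |
| 5/3.5/2.5% | 15%, plus loss | 12,557 | 9,728 | 2,829 (22.5%) |
| 5/3.5/2.5% | 20% then 15%, including loss | 12,557 | 9,877 | 2,680 (21.3%) |
| 5/3.5/2.5% | 20% then 15%, plus loss | 12,557 | 9,282 | 3,275 (26.1%) |
| 10/7/5% | 15%, including loss | 11,659 | 10,328 | 1,331 (11.4%) |
| 10/7/5% | 15%, plus loss | 11,659 | 9,096 | 2,563 (22.0%) |
| 10/7/5% | 20% then 15%, including loss | 11,659 | 9,848 | 1,811 (15.5%) |
| 10/7/5% | 20% then 15%, plus loss | 11,659 | 8,684 | 2,975 (25.5%) |
| 5/3.5/2.5% | 10/7/5%, including loss | 12,557 | 11,693 | 864 (6.9%) |

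These are patient-years, not deaths. They show how much collected follow-up the model sets aside, not how far a hazard ratio would move.

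**The case against.** The strongest reply is that the SAP is entitled to do this. Protocol 9 says of the SAP that "This document may modify the plans outlined in the protocol" and requires a protocol amendment only for major changes to the primary endpoint or its analysis. No non-inferiority rule in SAP 4.2 uses a secondary endpoint. The Protocol Summary sentence is itself closer to the SAP than to Protocol 9.2.2. All of this stands and limits the point to an undeclared departure between passages that must be reconciled.

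Protocol 9.2.2 is also loosely drafted: read literally, it asks for paired ITT and on-treatment analyses of reasons for discontinuation, which makes little sense. That does not affect the four adjudicated event endpoints.

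A 28-day window has some basis, since Protocol 8.2 ends active SAE reporting 28 days after the last dose. The same section, however, records adverse events on the CRF through the last subject visit, so the later data exist.

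Late deaths are not wholly out of sight. SAP 6.2 plans a listing and an incidence rate for all-cause deaths without stating a window, and SAP 8.2.1 says crude "incidence rates by Total Time, 60-Day On-Treatment Time and 28-Day On-Treatment Time analysis will be calculated as well". But that sentence sits under the primary analysis, SAP 8.2.2 opens by applying the 28-day rule to all events of interest, and neither a listing nor a crude rate is a total-time hazard ratio between randomised arms.

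Finally, Total Time mixes in later therapy. Protocol 13.6 allows standard of care to include tofacitinib, adalimumab or etanercept, which may dilute a difference between arms. On-treatment analysis is therefore defensible, particularly for opportunistic infections and hepatic events. That supports showing both analyses, as the protocol promised.

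**Conclusion.** The concern holds and should be fixed. The conflict between Protocol 9.2.2 and SAP 7.1.1 and 8.2.2 is explicit, covers four adjudicated endpoints, and is not recorded in the SAP's amendment table. All-cause mortality is the priority; the other three endpoints are mainly a matter of reconciliation.

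The illustrative share of follow-up excluded is 11.4% to 26.1% when the 15% discontinuation standard (with or without a higher first year) is used, and 6.9% when the MACE loss rates serve as the exit rate from treatment. This rests on a performance standard and planning assumptions rather than observed data, and on loss rates that the protocol states for the co-primary endpoints. The number of deaths affected and the effect on any hazard ratio cannot be derived from the documents.

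**What to change.** - In SAP 7.1.1 and 8.2.2, add Total Time Cox models and crude rates by randomised arm for all-cause mortality, and for adjudicated opportunistic infections, hepatic events and non-MACE cardiovascular events. Report them alongside the 28-Day On-Treatment results.
- In SAP 6.2, state the time window for the all-cause death incidence rate.
- Align the Protocol Summary sentence on secondary safety endpoints with Protocol 9.2.2.
- If the sponsor prefers on-treatment analysis alone for any of these endpoints, say so in the SAP as a departure from Protocol 9.2.2 and give the reason.

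The cost is SAP wording, one sentence in the Protocol Summary, and repeat runs of a definition already in SAP 7.1.1. No new data are needed. The downside is extra tables, and a Total Time result that has to be read with post-switch treatment in mind.

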 - Liver tests including Alanine Aminotransferase (ALT), Aspartate Transaminase (AST) and total bilirubin.

- *All-cause mortality (adjudicated)* (also known as all-cause deaths associated with the adjudicated primary endpoint criteria under Bullet Deaths below).

- *Reasons for permanent or temporary discontinuation of study medication.*

- *Concomitant drugs by treatment group, in the following categories:*
 - *Lipid Lowering Agents (LLA) including Statins;*
 - *DMARDS;*
 - *Steroids;*
 - *Analgesics and Nonsteroidal Anti-inflammatory Drug (NSAIDS);*

- *INH and Rifampacin.*
- *Laboratory Data Descriptive Statistics for the following tests:*
 - *Hemoglobin;*
 - *Platelets;*
 - *Creatine Kinase;*
 - *Serum Creatinine;*
 - *Total Cholesterol;*
 - *Low Density Lipoprotein Cholesterol (LDL-c);*
 - *High Density Lipoprotein Cholesterol (HDL-c);*
 - *Total Cholesterol/HDL-c Ratio;*
 - *Total Cholesterol/LDL-c Ratio;*
 - *Triglycerides.*
- *Vital Sign Descriptive Statistics Summaries, including BMI.*
- *Baseline Characteristics including:*
 - *Duration of Rheumatoid Arthritis (RA);*
 - *Cardiovascular Risk;*
 - *Subjects with Nodules, Sjogren's Syndrome, Anemia of Chronic Disease, Pulmonary manifestations;*
 - *Joints (JTS), CDAI, SDAI, Smoking History, Alcohol use.*
- *Deaths:*
 - *List of all-cause deaths associated with the adjudicated primary endpoint criteria;*
 - *List of all-cause deaths;*
 - *Incidence rate (95% CI) for all-cause deaths associated with the adjudicated primary endpoint criteria;*
 - *Incidence rate (95% CI) for all-cause deaths.*

- Patient Years exposure by treatment arm, including standard of care and by time point.

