7.1.1. Censoring Time for Time-to-event

There are three ways in defining the time to an event:

- The “60-Day On-Treatment Time” is the time from first study dose to an event observed while a subject is exposed to the study treatment plus the applicable attribution window. The 60-Day On-Treatment Time analysis will censor subjects who cross over from tofacitinib or TNFi to standard of care at 60 days after the last dose of randomized study drug.
- The “Total Time” is the time from first study dose to an event regardless whether the event occurs during on-treatment period or after the subject discontinues the study treatment and is still being followed. The Total Time analysis will not censor subjects who cross over from tofacitinib or TNFi to standard of care and will ascribe events to randomized treatments.
- The “28-Day On-Treatment Time” is the time from first study dose to an event observed while a subject is exposed to the study treatment plus the applicable attribution window. The 28-Day On-Treatment Time analysis will censor subjects who cross over from tofacitinib or TNFi to standard of care at 28 days after the last dose of randomized study drug.

More specifically, in time-to-event analyses for a given event, a subject’s time to event will be considered censored if any of the following conditions occurs prior to the subject experiencing the event in question:

- The subject is lost to follow-up (censoring time = study day of last on-study contact, eg, last visit, last lab test, and the like).
- The subject withdraws consent (censoring time = study day of last on-study contact).
- The subject is in the study under the protocol at the declared end of the study (censoring time = study day of last on-study contact).
- The subject dies without having experienced the event of interest (censoring time = study day of death).

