8.1.2. Analyses of Incidence Rates

Crude incidence rates will be reported as the total number of subjects with admissible events divided by the total (for all qualifying subjects) time at risk for the cohort/treatment group of interest. For subjects with events, the time at risk will be the time to the first event, for subjects without events, it will be the censoring time defined in [Section 7.1.1](#).

When subjects change regimens from study medication to standard of care then the following counting rules will be used to account for group changes in the estimation of crude incidence rates (where applicable):

- For MACE: there will be a 60-day risk window during which events will be attributed to both treatment groups, after which they will be assigned to the current treatment group.
- Malignancies (excluding NMSC): there will be a 60-day risk window during which events will only be attributed to the prior treatment group, after which they will be assigned to both treatment groups.

The 95% CIs for the crude incidence rate will be calculated for incidence rates based on the assumption that the actual count of cases arises from a Poisson distribution. The approach used in Daly et al.^{2,3} describing the calculation of exact confidence limits will be used. If x denotes the actual number of subjects with events, $(1 - \alpha)$ denotes the confidence level, x_L denotes the lower confidence limit and x_U denotes the upper confidence limit, then the following formula yields values for x_L and x_U ,

When $x > 0$,

$$x_L = 0.5 * \chi^2(2x; \alpha/2) \text{ and } x_U = 0.5 * \chi^2(2x+2; 1-\alpha/2),$$

When $x = 0$,

$$x_L = 0 \text{ and } x_U = 0.5 * \chi^2(2x+2; 1-\alpha/2).$$

In the above notation, $\chi^2(n; p)$ represents the p^{th} quantile of the chi-square distribution with n degrees of freedom.

Once x_L and x_U are obtained, they are to be adjusted for the at-risk population per 100 subject-years by multiplying by (100/total subject-years of event exposure).

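### Adjudicated non-melanoma skin cancer is analysed only to 28 days after last dose, so later adjudicated cases enter no planned hazard ratio or crude rate

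*SAP*

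**What the plan says.** SAP 6.2 lists adjudicated NMSC among the secondary safety endpoints, under adverse events. On the 28-Day On-Treatment Time, SAP 7.1.1 says: "It will be used for all the secondary safety endpoints, and the attribution window will be 28 days". Censoring is then at the earliest of last contact, death, or last dose plus 28 days. SAP 8.2.2 repeats the rule ("The 28-Day On-Treatment Time will be applied to all the events of interest"), names NMSC in its list of univariate Cox analyses, and adds crude rates without naming a different clock.

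Malignancies excluding NMSC are handled differently. Protocol 9.2.1 and SAP 8.2.1 make Total Time their principal analysis, and SAP 7.1.1 defines it so: "The Total Time analysis will not censor subjects who cross over from tofacitinib or TNFi to standard of care". Follow-up on that clock still ends at last contact or death.

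The remaining provisions on later events do not give NMSC an estimate:

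- SAP 8.2.1 plans crude "incidence rates by Total Time, 60-Day On-Treatment Time and 28-Day On-Treatment Time analysis will be calculated as well", but within the primary analysis, whose malignancy endpoint excludes NMSC.
- The regimen-change counting rules in SAP 8.1.2 cover MACE and one cancer endpoint: "Malignancies (excluding NMSC): there will be a 60-day risk window during which events will only be attributed to the prior treatment group".
- The overall standardized incidence ratio in SAP 8.1.2 excludes NMSC.
- The age subgroups in SAP 8.2.5 include other adjudicated events but name no clock, so SAP 7.1.1 governs.
- For subjects who switch to standard of care, SAP 8.2.2 says "a separate TEAE table will be presented for these subjects according to their initially randomized group". SAP 6.2 also plans "Patient Years exposure by treatment arm, including standard of care and by time point".

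**The concern.** The late cases will exist in the database. Protocol 6.2 keeps subjects in the study after they stop assigned drug, Protocol 8.2 records adverse events through the last subject visit, Protocol 8.6.1 names NMSC among events needing adjudication, and Protocol 9.7.4 sends basal and squamous cell cancers for central pathology review.

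The plan follows malignancy past drug discontinuation, yet the one cancer endpoint outside the co-primary gets no estimate by randomized arm for that period. An NMSC excess that persists, or is diagnosed late, after stopping drug would show only as counts in the post-switch table. A rough rate could be worked out by hand from those counts and the planned patient-years, but it would be neither an adjudicated rate nor a between-arm estimate.

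The two cancer results are also hard to set side by side. They share 28-day crude rates. They share no Total Time rate and no clock for hazard ratios, because the 28-day Cox list in SAP 8.2.2 contains NMSC but not the other malignancies.

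**Working it through.** **Check of the design inputs.** Protocol 9.1 asks for 138 malignancies (90% power) and 103 MACE (80% power) to exclude a hazard ratio (HR) of 1.8 with 2:1 allocation. Schoenfeld's formula, (z₀.₉₇₅ + z_power)² / [(1/3)(2/3)(ln 1.8)²], gives 10.507/0.0768 = 136.8, so 137, and 7.849/0.0768 = 102.2, so 103. Accrual of 1000/1500/1500 over three years, a 5-year study, malignancy loss to follow-up of 5%, 3.5% and then 2.5% per year, and 1.1 events per 100 patient-years (PY) give 12,322 PY and 135.5 malignancies, close to the 138 planned. The follow-up model therefore agrees with the protocol's own.

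**Follow-up beyond last dose + 28 days.** With S_L the probability of not being lost and S_D the probability of still being on drug, averaged over entry times:

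- Total Time per subject = ∫ S_L(t) dt = 3.139 years. Times 4000, this is 12,557 PY (not truncated at the event).
- 28-day clock per subject = ∫ S_L(t) · S_D(t − 28 days) dt.

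The documents allow three readings of drug discontinuation:

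- **A:** the 15% per year in Protocol 13.7 comes on top of loss to follow-up.
- **B:** the 15% already includes study withdrawal.
- **C:** the 10/7/5% MACE loss in Protocol 9.1 is all on-treatment loss.

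The standard error (SE) ratio for the log HR is √(Total Time years / 28-day years).

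| Reading | 28-day years | PY excluded | Share | SE ratio |
|---|---|---|---|---|
| A | 2.432 | 2,829 | 22.5% | 1.136 |
| B | 2.590 | 2,198 | 17.5% | 1.101 |
| C | 2.923 | 864 | 6.9% | 1.036 |

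Replacing the 15% in reading A by 10% or 20% gives 15.6% or 29.0%.

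**Cases left out.** The documents give no NMSC rate, so 0.3, 0.5 and 0.8 per 100 PY are assumed, the same on and off drug and with no treatment effect. Excluded PY × rate gives:

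| Reading | 0.3 | 0.5 | 0.8 |
|---|---|---|---|
| A | 8 | 14 | 23 |
| B | 7 | 11 | 18 |
| C | 3 | 4 | 7 |
| All cases on Total Time | 38 | 63 | 100 |

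**Precision at 0.5 per 100 PY, HR 1, combined tofacitinib versus TNFi.** SE = √(1/d_TNFi + 1/d_tofa), and the upper 95% limit is exp(1.96 × SE). On Total Time, 1333 × 3.139 × 0.005 = 20.9 TNFi and 41.8 tofacitinib cases, SE 0.268, limit 1.69. On the 28-day clock under A, 16.2 and 32.4 cases, SE 0.304, limit 1.82. Readings B and C give 1.78 and 1.72.

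**Chance that the interval excludes 1.** Take 0.5 per 100 PY in the TNFi arm and an assumed on-drug HR of 2.0. The chance is Φ(ln HR / SE − 1.96). The Total Time HR is the patient-year-weighted mix of on-drug and off-drug HRs.

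| Reading | 28-day | Total Time, off-drug HR 2.0 | 1.5 | 1.0 |
|---|---|---|---|---|
| A | 70.4% | 81.0% | 73.4% | 64.0% |
| B | 73.1% | 81.0% | 75.2% | 68.4% |
| C | 78.1% | 81.0% | 78.8% | 76.5% |

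Total Time has the higher chance only if the off-drug HR exceeds about 1.33 to 1.35.

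**The case against.** The strongest reply is that the SAP follows the protocol. The Protocol Summary has secondary safety endpoints summarized by treatment received when the event occurs, and Protocol 9.2.2 says the same of adverse events, where the SAP places NMSC. Protocol 9.2.2 promises both ITT and on-treatment analyses for other secondary endpoints, but the list in Protocol 2.2.1.2 does not name NMSC. The post-discontinuation rationale in Protocol 9.1 and 9.2.1 is given for malignancy excluding NMSC, and neither document claims a carry-over effect for skin cancer. All of this stands: no commitment is broken.

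It is also fair that a gain in power is not shown. If the effect stops with the drug, Total Time dilutes it. Standard of care may itself be tofacitinib, adalimumab or etanercept (Protocol 13.6), so a late case can be credited to one arm while the subject takes another study drug.

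The 22.5% is the largest of the three main readings. Protocol 13.7 derives its 15% from overall discontinuation rates and counts unwillingness to continue among the components, which favours 17.5%; the MACE loss figures support 6.9%. The whole range should be carried.

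These points argue against replacing the 28-day analysis. They do not remove the gap: late adjudicated cases have no planned estimate by arm, and the descriptive table does not supply one.

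**Conclusion.** The concern holds as a minor point, worth considering. On the text, adjudicated NMSC has one clock, and no Total Time or 60-day hazard ratio or crude rate for it appears in either document. About 7% to 23% of planned follow-up lies outside the window, and so does the same share of cases if the NMSC rate is constant over time and equal on and off drug. The shares rest on the protocol's accrual, loss and discontinuation assumptions and a 5-year study. Case counts, confidence limits and detection probabilities rest further on assumed NMSC rates and hazard ratios. The primary conclusion is unaffected, since the decision rules in SAP 4.2 use only MACE and malignancy excluding NMSC. The case rests on completeness and on comparability with the other malignancies.

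**What to change.** In SAP 7.1.1 and 8.2.2, add for adjudicated NMSC a supplementary univariate Cox analysis on Total Time and a Total Time crude incidence rate, both by randomized treatment. Report them beside the 28-Day On-Treatment result, which stays as it is.

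The cost is a few lines of SAP text, one model and one rate table, on data already collected and adjudicated. The drawback should be stated with the result: Total Time includes time on standard of care. If the off-drug HR is 1.0, an on-drug HR of 2.0 becomes 0.775 × 2.0 + 0.225 × 1.0 = 1.78 under reading A, and about 1.82 and 1.93 under B and C. The new analysis should therefore supplement the 28-day one and not replace it.
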